### **Amendment 02** (Date: 06 Dec 2023)

This amendment is considered to be substantial based on the criteria set forth in Article 10(a) of Directive 2001/20/EC of the European Parliament and the Council of the European Union and EU Regulation No 536/2014.

#### **Overall Rationale for the Amendment:**

The overall rationale for Amendment 02 was to incorporate clarifying content from an EU-specific amendment into a global protocol. In addition, the analysis plan was updated to bring the Type I error rate in line with the nominal value. A description of changes is provided below. Minor editorial changes have not been summarized in the table.

Section # and Name	Description of Change	Brief Rationale

 
Synopsis
 
Schema
 
4.1. Overall Design
 
4.2. Scientific Rationale for Study Design
 
6.9. Concomitant Therapy
 
9.3.1.1. Definitions of Study Periods for Analysis
 
	Content from Appendix 5 (Country-Specific Requirements) of Amendment 01/EU 1 was incorporated into the body of the global protocol.	Clarifications.

Section # and Name	Description of Change	Brief Rationale

 
9.3.2. Primary Endpoint
 
9.3.4. Exploratory Endpoints
 
9.5. Sample Size Determination
 
10.1.1. Regulatory and Ethical Considerations
 
10.1.4. Data Protection
 
Appendix 1. References
 
		

 
9.1.1. Multiplicity Adjustment
 
9.4. Interim Analysis
 
9.5 Sample Size Determination
 
Appendix 1. References
 
	The prespecified alpha levels were modified to bring the Type I error rate in line with the nominal value.	Correction; results from simulation analyses suggested the Type I error rate was higher than expected.

#### **Amendment 01/EU 01 (Date: 06 Nov 2023)**

This EU-specific amendment is considered to be nonsubstantial based on the criteria set forth in Article 10(a) of Directive 2001/20/EC of the European Parliament and the Council of the European Union and EU Regulation No 536/2014.

#### **Overall Rationale for the Amendment:**

The overall rationale for the changes implemented in Amendment 01/EU 1 was to provide clarification in response to comments from EU member states via CTIS. Minor editorial changes have not been summarized. A description of changes is provided below.

Section # and Name	Description of Change	Brief Rationale
Appendix 5. Country-Specific Requirements Note: Protocol Amendment History was moved to Appendix 6.	
A new appendix was added with EU-specific clarifications for the following sections of the protocol:
 
 
Section 1.1. Synopsis
 
Section 1.2 Schema
 
Section 4.1. Overall Design
 
Section 4.2. Scientific Rationale for Study Design
 
Section 6.9. Concomitant Therapy
 
Section 9. Statistical Considerations
 
Section 10.1.1. Regulatory and Ethical Considerations
 
Section 10.1.4. Data Protection
 
Appendix 1. References
 
	For clarification in response to CTIS comments.

**Amendment 01** (Date: 29 Mar 2023)

**Overall Rationale for the Amendment:**

The overall rationale for the changes implemented in the protocol amendment 01 was to change the phase of the study stated in the protocol from Phase 4 to Phase 3/Phase 4. The protocol was amended to clarify that in regions where the study drug XYWAV follows approved label, the protocol is a Phase 4 interventional study, and in regions where XYWAV does not follow approved label, the protocol is a Phase 3 study. Minor editorial changes for clarity are not included in the table below.

Section # and Name	Description of Change	Brief Rationale
Title Page, Synopsis and Section 4.1 Overall Study Design	Changed the phase in the protocol from Phase 4 to Phase 3/Phase 4 and added an explanation of the phase difference in regions where XYWAV follows approved label.	The purpose of this change is to clarify the phase of this study protocol for regions where XYWAV follows approved label.

## **1. INTRODUCTION**

The purpose of this statistical analysis plan (SAP) is to describe in detail the statistical methodology and planned analyses to be conducted for Protocol JZP258-406; the current version is based on Protocol v4.0 dated 17 May 2024. Additional analyses or substantial revisions from the analyses outlined in this plan will be documented with rationale in the final CSR.

JZP258-406 is a Phase 3/Phase 4, multicenter, single-arm, open-label switch study. The study will enroll individuals diagnosed with Type 1 or Type 2 narcolepsy [REDACTED].

XYWAV (calcium, magnesium, potassium, and sodium oxybates) oral solution was developed as an alternative, low-sodium formulation of XYREM (high sodium oxybate) and contains the same active moiety, oxybate (GHB), as XYREM. By formulating oxybate with a mixture of cations, XYWAV has 92% less sodium than XYREM in the anticipated dose range of 6 to 9 g nightly.

The aim of this study is to quantify the change in 24-hour average SBP when participants with narcolepsy treated with high-sodium oxybate are transitioned to XYWAV. It is hypothesized that there will be a clinically relevant reduction of SBP after switching from high-sodium oxybate to XYWAV. The results of this study are anticipated to provide healthcare providers, patients, and payers with important new information regarding BP changes related to differences in sodium content between available oxybates for the treatment of narcolepsy.

## **2. STUDY OBJECTIVES AND ENDPOINTS**

### **2.1. Study Objectives**

#### **2.1.1. Primary Efficacy Objective(s)**

- Evaluate the impact of switching from high-sodium oxybate to XYWAV on 24-hour ambulatory SBP for participants with narcolepsy.

#### **2.1.2. Secondary Efficacy Objective(s)**

- Evaluate the impact of switching from high-sodium oxybate to XYWAV on daytime ambulatory SBP for participants with narcolepsy
- Evaluate the impact of switching from high-sodium oxybate to XYWAV on seated resting SBP for participants with narcolepsy
- Evaluate the impact of switching from high-sodium oxybate to XYWAV on nighttime SBP for participants with narcolepsy.

#### **2.1.3. Exploratory Efficacy Objective(s)**

- Evaluate the impact of switching from high-sodium oxybate to XYWAV on ambulatory DBP for participants with narcolepsy;
- Evaluate the impact of switching from high-sodium oxybate to XYWAV on seated resting DBP for participants with narcolepsy;

- Evaluate the impact of switching from high-sodium oxybate to XYWAV on daytime-nighttime DBP decline (dipping) in participants with narcolepsy;
- Evaluate the relationship between BP and urine sodium excretion;
- Evaluate the impact of switching from high-sodium oxybate to XYWAV on participant-reported change in conditions in participants with narcolepsy;
- Evaluate the impact of switching from high-sodium oxybate to XYWAV on participant-reported severity of conditions in participants with narcolepsy;

#### 2.1.4. Safety Objective

- Evaluate safety in participants switching from high-sodium oxybate to XYWAV.

## 2.2. Study Endpoints

### 2.2.1. Primary Endpoint

- Change from baseline to EOT Visit on the 24-hour average SBP (mm Hg)

### 2.2.2. Secondary Endpoints

- Change from baseline to EOT Visit on the daytime average SBP (mm Hg)
- Change from baseline to EOT Visit on the seated resting average SBP (mm Hg)
- Change from baseline to EOT visit on nighttime average SBP (mm Hg)

### 2.2.3. Exploratory Endpoints

[REDACTED]  
[REDACTED]  
[REDACTED]  
[REDACTED]

#### **2.2.4. Safety Endpoints**

- Overall TEAEs
- TEAEs by maximum severity
- TEAEs related to study intervention
- Serious TEAEs
- TEAEs leading to discontinuation
- Fatal TEAEs

### **3. STUDY DESIGN**

#### **3.1. Summary of Study Design**

This is a Phase 3/Phase 4, multicenter, single-arm, open-label switch study. In regions where XYWAV follows approved label, the study is a Phase 4 interventional study, and in regions where XYWAV does not follow approved label, the study is a Phase 3 study. The study will enroll patients with Type 1 or Type 2 narcolepsy [REDACTED]  
[REDACTED].

To establish adequate exposure to high-sodium oxybate and well-tolerated treatment regimen, participants will be required to be on 6 to 9 g/night of high-sodium oxybate for at least 6 consecutive weeks before screening. After all other eligibility criteria have been assessed (except for clinical laboratory results obtained at screening), the 24-hour BP recording can be initiated, and the 24-hour urine collection obtained as baseline.

After all screening assessments have been completed, eligible participants will switch, on a gram-for-gram basis, from high-sodium oxybate (e.g., XYREM) to XYWAV. This switch must occur no more than 2 weeks after the 24-hour ambulatory BP recording.

After approximately 6 weeks of treatment with XYWAV, the 24-hour BP recording and 24-hour urine collection, along with other measurements will be repeated during the EOT Visit.

Study participation will end following a Safety Follow-Up Visit.

[figure not shown]
#### **3.2. Study Treatment**

The study duration for each participant will be up to approximately 11 weeks. The study includes the following study periods:

- A Screening Period (up to 3 weeks): All subjects will be evaluated for eligibility during the screening period, which will occur over a period of up to 3 weeks.

- An Intervention Period (approximately 6 weeks): this period is initiated by the switch from 6 to 9 g/night of high-sodium oxybate to the same (gram-per-gram) dose of XYWAV and includes approximately 6 weeks of treatment with the study intervention (XYWAV) and an EOT Visit.
  - Participants will continue taking study intervention until the EOT 24-hour BP recording meets minimum data quality standards. If needed, participants may repeat the EOT 24-hour BP recording up to 2 additional times, which would increase the duration of the Intervention Period and, consequently, the overall duration of study participation.
  - After completing an EOT 24-hour BP recording that meets minimum data quality standards, participants may transition to commercial XYWAV (as permitted by local health authorities) or other standard of care per physician discretion.
- A Safety Follow-up Visit (to be scheduled at least 14 days after the last dose of study intervention).

In this study, given the effects of some concomitant medicines on BP, participants who take stimulants and/or alerting agents or other medications known to affect BP are required to maintain doses unchanged from at least 2 months before study entry to the end of the study; participants who take antihypertensives at study entry must agree to maintain their treatment at the same dose throughout the study unless otherwise advised by their medical care provider. Any changes to these therapies during the study will be reported.

### 3.3. Power and Sample Size Considerations

There are no historical data on 24-hour average BP changes in participants switching from high-sodium oxybate to XYWAV. Given the limited information, data from other studies with drugs similar to oxybate were leveraged to inform the design of this study. It was determined that an

effect size of 3.0 or 3.5 with a SD range from 7.0 to 8.0 will be considered for power and sample size calculations. Sample sizes for different scenarios (different effect sizes and SD) were calculated with a one-sided significance level of 0.025 (Table 2).

A preselected target sample size of 57 will provide 90% power to detect a mean 24-hour average SBP difference of 3.5 mm Hg between baseline and the EOT Visit after switching from high-sodium oxybate to XYWAV for 6 weeks, assuming an SD of 8.0 points.

This study will use a 2-stage group sequential design in which the final sample size may be adaptively determined. The primary endpoint will be evaluated at a planned interim analysis, with the option to terminate enrollment if the primary endpoint is met, or to adaptively modify the final study sample size if the primary endpoint is not met (see Section 3.5).

Assuming a 15% discontinuation/withdrawal rate during the Intervention Period, a minimum of 67 (up to approximately 91) participants will be recruited to initiate the switch to XYWAV and to capture complete data. Assuming a 60% screen failure rate during the Screening Period, a minimum of 170 (up to approximately 230) study participants will be enrolled (sign the ICF) into the study.

**Table 2. Power and Sample Size Calculations**

Effect Size	Standard Deviation	80% Power	85% Power	90% Power
3.0	7.0	45	51	60
3.5	7.0	34	38	44
3.0	7.5	52	59	68
3.5	7.5	39	44	51
3.0	8.0	58	66	77
3.5	8.0	43	49	57

### 3.4. Randomization and Blinding

This is an open-label study with no randomization or blinding.

### 3.5. Interim Analysis

The interim analysis will be performed after 43 participants (75%) have completed the study. Using the sample size assumptions described in Section 3.3, the calculated O'Brien-Fleming one-sided alpha levels for statistical significance are 0.00998 for the interim analysis and 0.02194 for the final analysis. If the primary endpoint is not rejected at the interim analysis, the final sample size will be adaptively determined based on conditional power.

Conditional power refers to the probability of reaching statistical significance at the final analysis given the data obtained at the interim analysis, and it is calculated according to equation (1):

$$CP = 1 - \Phi\left(\frac{z_{\alpha}\sqrt{n_2} - z_1\sqrt{n_1}}{\sqrt{\tilde{n}_2}} - \frac{z_1\sqrt{\tilde{n}_2}}{\sqrt{n_1}}\right) \quad (1)$$

Where:

$\Phi(\bullet)$  is the standard normal cumulative distribution function

$n_1$  = actual sample size at interim analysis (expected to be  $n_1 = 43$ )

$n_2$  = planned sample size at final analysis (i.e.,  $n_2 = 57$ )

$\tilde{n}_2$  = sample size increment between interim and planned final analyses (expected to be  $\tilde{n}_2 = 14$ )

$z_\alpha$  = the standard normal value for a type I error rate of  $\alpha$ ; i.e.  $\Phi(1-0.025)=1.95996$

$z_1 = \bar{x}_1 / se(\bar{x}_1)$ , the z-statistic for 24-hour SBP change from baseline computed at interim analysis

Given the conditional power, the final sample size target will then be determined using a "promising zone" approach:

- If  $CP \geq 90\%$  (Favorable zone): Continue enrolling more participants until prespecified target sample size ( $N = 57$ ).
- If  $CP < 40\%$  (Unfavorable zone): Continue enrolling more participants until prespecified target sample size ( $N = 57$ ).
- If  $40\% \leq CP < 90\%$  (Promising zone): Calculate additional sample size  $\tilde{n}'_2$  based on formula (2). The final sample size target will be adjusted to  $\min(77, n_1 + \tilde{n}'_2)$ .

$$\tilde{n}'_2 = \left( \frac{n_1}{z_1^2} \right) \left[ \frac{z_\alpha \sqrt{n_2} - z_1 \sqrt{n_1}}{\sqrt{n_2} - \sqrt{n_1}} + z_\beta \right]^2 \quad (2)$$

Where:

$n_1$  = actual sample size at interim analysis (expected to be  $n_1 = 43$ )

$n_2$  = planned sample size at final analysis (i.e.,  $n_2 = 57$ )

$z_\alpha$  = the standard normal value for a type I error rate of  $\alpha$ ; i.e.  $\Phi(1-0.025)=1.95996$

$z_\beta$  = the standard normal value for a type II error rate of  $\beta$ ; i.e.  $\Phi(1-0.10)=1.28155$

$z_1 = \bar{x}_1 / se(\bar{x}_1)$ , the z-statistic for 24-hour SBP change from baseline computed at interim analysis

Mehta and Pocock reviewed the methodology demonstrating that the promising zone adaptive design maintains the type I error probability if the sample size is increased only when the conditional power falls into the promising zone.

Enrollment may continue while the interim analysis is being performed. To mitigate the risk of enrolling more participants than needed (i.e., "overruns"), the interim analysis will be based on the primary endpoint only, which will shorten the time needed to perform the analysis. However, all participants meeting analysis set criteria will be analyzed, regardless of the final sample size target.

---

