2. “Promising zone”: If  $40\% \leq$  conditional power  $< 90\%$ , increase the target sample size to  $(43 + \tilde{n}'_2)$ , up to a maximum of 77 completers.
3. “Unfavorable zone”: If conditional power  $< 40\%$ , continue enrolling participants until the prespecified target sample size ( $N = 57$ ).

When the conditional power falls into the “promising zone”, the additional sample size required is calculated as follows (Mehta, 2011, equation 9):

$$\tilde{n}'_2 = \left(\frac{n_1}{z_1^2}\right) \left[\frac{z_{\alpha}\sqrt{n_2} - z_1\sqrt{n_1}}{\sqrt{n_2 - n_1}} + z_{\beta}\right]^2$$

Where:

$n_1$  = actual sample size at interim analysis (expected to be  $n_1 = 43$ )

$n_2$  = planned sample size at final analysis (i.e.,  $n_2 = 57$ )

$z_{\alpha}$  = the standard normal value for a type I error rate of  $\alpha$ ; ie,  $\Phi(1 - 0.025) = 1.95996$

$z_{\beta}$  = the standard normal value for a type II error rate of  $\beta$ ; ie,  $\Phi(1 - 0.10) = 1.28155$

$z_1 = \bar{x}_1 / se(\bar{x}_1)$ , the z-statistic for 24-hour SBP change from baseline computed at interim analysis

The favorable zone threshold was set to the target study power (90%; [Mehta, 2011](#)). Based on the study parameters, the unfavorable zone threshold was determined to be approximately 40% ([Mehta, 2011](#), equations 10 to 12).

Enrollment will continue while the interim analysis is being performed. To mitigate the risk of enrolling more participants than needed (ie, “overruns”), the interim analysis will be conducted using the primary endpoint only, which will shorten the time needed to perform the analysis. However, all participants meeting analysis set criteria will be included in the final study report, regardless of the adaptive sample size target.

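### The sample-size re-estimation formula in SAP 3.5 has a different denominator from Protocol 9.4 and does not follow from the SAP's own conditional-power equation; targets differ for conditional power of about 75% to 90%, by up to 14 completers

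*SAP*

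**What the plan says.** Both documents plan an interim analysis at 43 completers and compute conditional power for the planned final size of 57. If conditional power is at least 40% but below 90%, they re-estimate the number still to be recruited, with a ceiling of 77 completers. The SAP introduces this step as "Promising zone): Calculate additional sample size".

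The inputs agree between the documents. In SAP 3.5 they are:
- n1: "actual sample size at interim analysis (expected to be $n_1 = 43"
- n2: "planned sample size at final analysis (i.e., $n_2 = 57"
- planned increment: "sample size increment between interim and planned final analyses (expected to be $\tilde{n}_2 = 14"
- z_alpha: "i.e. $\Phi(1-0.025)=1.95996"
- z_beta: "i.e. $\Phi(1-0.10)=1.28155"

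The formulas for the additional sample size do not agree. As read from the PDFs, the relevant fragments are:
- SAP 3.5, equation (2): "z_1 \sqrt{n_1}}{\sqrt{n_2} - \sqrt{n_1}} + z_\beta"
- Protocol 9.4: "z_1\sqrt{n_1}}{\sqrt{n_2 - n_1}} + z_{\beta"

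The SAP has two separate roots joined by a minus sign; the protocol has one root over the difference. SAP 5.6 declares no change to the planned analyses, and the modification history in SAP 11 mentions no change to this formula.

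**The concern.** For the same interim result the two documents can require different final sample sizes, so the adaptation is not uniquely prespecified: whichever formula is programmed, the other document is breached. Protocol 9 describes the SAP as the more technical and detailed account, so the SAP version is the likelier one to be coded. The choice would take effect once interim efficacy results are known, in an open-label single-arm trial for which no data monitoring committee is planned. The smaller SAP denominator enlarges the first term in the bracket by 3.742 / 0.992 = 3.77 times. That pushes the target upward and leads to more people being consented and switched than the protocol rule asks for.

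**Working it through.** **Inputs.** n1 = 43, n2 = 57, increment 14, z_alpha = 1.95996, z_beta = 1.28155, cap 77 (SAP 3.5 and Protocol 9.4). z1 is taken as positive for a fall in blood pressure, and increments are rounded up; both are my conventions.

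**The plan's own figures.** A one-sample t-test with one-sided alpha 0.025, difference 3.5 and SD 8 gives N = 57 with power 90.08%. All 18 cells of the power table reproduce. The O'Brien-Fleming levels 0.00998 and 0.0219 reproduce at information fraction 0.75. Neither document gives a worked value of the re-estimation formula, so I tested it against equation (1).

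**Which form follows from equation (1).** Write a = z_alpha√n2 − z1√n1. Equation (1) is CP = 1 − Φ(a/√14 − z1√14/√n1). Hold the first term at its planned value and let the increment in the second term be m. For CP = 90%:

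a/√14 − z1√m/√n1 = −z_beta, so m = (n1/z1²)[a/√14 + z_beta]².

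Since 14 = n2 − n1, this is the protocol form. Its denominator is √14 = 3.742. The SAP denominator is √57 − √43 = 7.550 − 6.557 = 0.992.

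**Worked case, z1 = 2.10.** a = 1.95996 × 7.550 − 2.10 × 6.557 = 14.797 − 13.771 = 1.027, and n1/z1² = 43/4.41 = 9.751.
- Protocol: 9.751 × (1.027/3.742 + 1.28155)² = 9.751 × 1.556² = 23.6. Target 43 + 24 = 67.
- SAP: 9.751 × (1.027/0.992 + 1.28155)² = 9.751 × 2.316² = 52.3. Then 43 + 53 = 96, capped at 77.

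Put into the second term only, the protocol increment returns CP = 0.900 and the uncapped SAP increment returns 0.979.

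**Across the zone.** Conditional power of 40% to 90% corresponds to z1 = 1.593 to 2.254, all below the interim efficacy boundary of 2.327.

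| z1 | CP at N = 57 | Protocol increment | Protocol target | SAP increment | SAP target | Gap |
|---|---|---|---|---|---|---|
| 1.80 | 0.590 | 57.5 | 77 | 245.2 | 77 | 0 |
| 2.00 | 0.755 | 32.2 | 76 | 95.3 | 77 | 1 |
| 2.05 | 0.790 | 27.6 | 71 | 71.7 | 77 | 6 |
| 2.10 | 0.822 | 23.6 | 67 | 52.3 | 77 | 10 |
| 2.15 | 0.851 | 20.1 | 64 | 36.7 | 77 | 13 |
| 2.16 | 0.856 | 19.4 | 63 | 34.0 | 77 | 14 |
| 2.20 | 0.876 | 16.9 | 60 | 24.3 | 68 | 8 |
| 2.25 | 0.898 | 14.2 | 58 | 14.9 | 58 | 0 |

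The protocol form reaches the cap up to z1 = 1.992, which is (1.992 − 1.593)/0.661 = 60% of the zone. The SAP form reaches it up to 2.163, which is (2.163 − 1.593)/0.661 = 86%. Targets differ over about 39% of the zone, from conditional power of about 75% to just under 90%.

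**How often.** Take z1 as normal with variance 1 and mean (3.5/8)√43 = 2.87. Then 16.8% of trials fall in the zone and 46% of those get a different target: 0.168 × 0.46 = 7.8% of all trials. Among these the mean excess is 7.6 completers; averaged over all trials it is 0.59. Within the zone the cap is reached in 83% (SAP) against 53% (protocol). With a true effect of 3.0 mm Hg, 9.7% of trials are affected; with no effect, 1.1%.

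**In participants.** At the plan's 15% discontinuation and 60% screen failure, 7.6 extra completers mean 7.6/0.85 = 8.9 more switched and 8.9/0.40 = 22 more consented. The largest gap of 14 means about 16 and 41.

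**The case against.** **The difference may be a reading artefact.** It rests on how far one root sign extends in a machine-read equation. Everything else in the two sections matches and no change is declared, so a transcription or conversion slip is plausible. This stands as a reason to look at the SAP PDF first. The extracted text does show two separate roots.

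**A reader might infer that the error alone sends most promising results to 77.** The documents do not support that. The protocol form already gives 77 over about 60% of the zone. The SAP form adds about 26 percentage points, and below conditional power of about 75% the cap makes the two targets identical.

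**A reader might infer inflated Type I error.** That is not supported either. Both forms act in the same zone under the same cap, and both documents argue that an increase confined to that zone preserves the error rate. The alpha levels and the final test are unchanged.

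**The SAP's surplus depends on how equation (1) is read.** The protocol form delivers 90% only with the first term held at n2 = 57 and increment 14. If the new N is entered throughout equation (1), the protocol increment at z1 = 2.10 gives 0.864, and 90% would need about 78 completers, close to the SAP's 77. At z1 = 2.20 about 66 are needed, against 60 (protocol) and 68 (SAP). This is a fair limit on calling the extra completers unnecessary. It does not rescue the SAP form, which follows from neither reading: uncapped, it asks for 96 at z1 = 2.10.

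**The effect is small and already budgeted.** The plan provides for 77 completers, 91 treated and 230 consented. That is true, and it limits the harm. It does not settle which target applies.

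**Conclusion.** The concern holds in a limited form. As the text stands, SAP equation (2) contradicts Protocol 9.4 and does not follow from SAP equation (1); the protocol form does, with the first term of equation (1) held at its planned values. Measured against that form, the SAP target is up to 14 completers too high when conditional power is about 75% to 90%. It is the same when conditional power is below about 75%, because both reach the cap.

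The shares of 86% and 60% are shares of the z1 range, not probabilities. The figure of about 8% of trials assumes a true effect of 3.5 mm Hg, SD 8, an interim at exactly 43 completers and a normal z1. Replacing 1.95996 with the value for the final level 0.02194 (2.015) changes little: the cap is reached over 88% against 60% of the zone, and the largest gap is 15. The conclusion is conditional on the SAP PDF showing the same two roots.

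**What to change.** Confirm the extent of the root sign in the SAP PDF. If it reads as extracted, replace the denominator in SAP 3.5 equation (2) with √(n2 − n1), as in Protocol 9.4, and record the correction in the SAP modification history. Do this before the interim program is run.

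If a program check is added, specify it exactly: keep the first term of equation (1) at n2 = 57 and increment 14, put the uncapped, unrounded re-estimated increment into the second term only, and confirm that the result is 90%. Replacing the increment in both terms would wrongly fail the protocol formula: at z1 = 2.10 it returns 0.911, or 0.864 if n2 is updated as well.

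The cost is a one-term SAP correction and, optionally, one line of validation code. No participants are added, and the zones, cap and alpha levels stay as they are.

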### **4.4. End of Study Definition**

A participant is considered to have completed the study if they have completed all periods of the study, including the last scheduled procedure shown in the SoA (Section 1.3).

The end of the study is defined as the date of the last visit of the last participant in the study.

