## 9.4. Interim Analysis

A 2-stage group sequential design with sample size re-estimation is used for this study. An interim analysis will be performed after 43 participants (75%) have completed the study. This interim analysis will include a binding stopping rule for efficacy if the primary endpoint (specified in Section 3) is met. Using the sample size assumptions described in Section 9.5, the

calculated O'Brien-Fleming alpha level for statistical significance on the primary endpoint is 0.00998 for the interim analysis.

If the primary endpoint does not reach the necessary significance level for early termination at the interim analysis, study enrollment will continue and the final sample size will be adaptively determined using a “promising zone” approach (Mehta, 2011). Based on the observed effect size at the interim analysis, the conditional power (ie, probability of reaching statistical significance at the final analysis given the data obtained at the interim) for the primary endpoint will be calculated. Because the Type I error probability is not inflated when using conditional power and the promising zone methodology used in this study to determine the situations in which the sample size can be increased (Mehta, 2011), no further adjustment to the O'Brien-Fleming boundaries (described in Section 9.1.1) is required for the final analysis.

The conditional power is calculated as follows (Mehta, 2011, equation 6):

$$CP = 1 - \Phi\left(\frac{z_{\alpha}\sqrt{n_2} - z_1\sqrt{n_1}}{\sqrt{\tilde{n}_2}} - \frac{z_1\sqrt{\tilde{n}_2}}{\sqrt{n_1}}\right)$$

Where:

$\Phi(\bullet)$  is the standard normal cumulative distribution function

$n_1$  = actual sample size at interim analysis (expected to be  $n_1 = 43$ )

$n_2$  = planned sample size at final analysis (ie,  $n_2 = 57$ )

$\tilde{n}_2$  = sample size increment between interim and planned final analyses (expected to be  $\tilde{n}_2 = 14$ )

$z_{\alpha}$  = the standard normal value for a type I error rate of  $\alpha$ ; ie,  $\Phi(1 - 0.025) = 1.95996$

$z_1 = \bar{x}_1 / se(\bar{x}_1)$ , the z-statistic for 24-hour SBP change from baseline computed at interim analysis

Based on the calculated conditional power, one of the following 3 actions will be taken:

1. “Favorable zone”: If conditional power  $\geq 90\%$ , continue enrolling participants until the prespecified target sample size ( $N = 57$ ).

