## 5.4. Level of Significance & Multiplicity Adjustment

To control family-wise error rate inflation due to multiple endpoints and the interim analysis (Section 3.5), a fixed hierarchical testing sequence will be employed. Testing begins with the first endpoint at the specified alpha level and continues through the sequence until an endpoint is not statistically significant. Remaining analyses will be considered exploratory and associated p-values will be considered nominal.

The Type I error rate for study endpoints will be set at a one-sided level of 0.025. To account for the possibility of ending the study at the interim analysis, statistical significance for the primary endpoint (#1) will be assessed using O'Brien-Fleming one-sided alpha levels of 0.00998 for the interim analysis and 0.02194 for the final analysis. Statistical significance for each of the secondary endpoints (#2 to #4) will be assessed using the Pocock one-sided alpha level of 0.0168 at either the interim or final analysis.

Statistical hypotheses to be tested (in sequential order):

1. Change in the 24-hour average SBP (mm Hg) following 6 weeks of XYWAV treatment after switching from high-sodium oxybate in participants with narcolepsy
2. Change in the daytime average SBP (mm Hg) following 6 weeks of XYWAV treatment after switching from high-sodium oxybate in participants with narcolepsy
3. Change in the seated resting average SBP (mm Hg) following 6 weeks of XYWAV treatment after switching from high-sodium oxybate in participants with narcolepsy
4. Change in the nighttime average SBP (mm Hg) following 6 weeks of XYWAV treatment after switching from high-sodium oxybate in participants with narcolepsy

Analyses not part of this hierarchy will be considered exploratory, and no multiplicity adjustment will be performed. P-values reported in standard table outputs will be considered nominal.

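### The final level of 0.02194 is set for an interim at about 75% of 57 completers, but overrun can raise the final number in any zone and no rule recomputes the level.

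*SAP*

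**What the plan says.** SAP 5.4 fixes the overall error rate: "The Type I error rate for study endpoints will be set at a one-sided level of 0.025". SAP 3.5 gives the two levels for the primary endpoint as "0.00998 for the interim analysis and 0.02194 for the final analysis", and places the interim as follows: "The interim analysis will be performed after 43 participants (75%) have completed the study". Protocol 9.1.1 and 9.4 use the same levels and timing.

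If the interim boundary is not crossed, conditional power decides the final target. The target is 57 below 40% and at or above 90%; between those limits it rises to at most 77. SAP 3.5 says this preserves the Type I error "if the sample size is increased only when the conditional power falls into the promising zone". Protocol 9.4 relies on the same result to say that the boundaries need no further correction at the final analysis.

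Both sections then deal with overrun. Enrolment will (Protocol) or may (SAP) go on while the interim is prepared. The only mitigation is to limit the interim to the primary endpoint. The SAP adds that "all participants meeting analysis set criteria will be analyzed, regardless of the final sample size target"; Protocol 9.4 similarly includes everyone in the final report.

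**The concern.** The condition and the overrun rule sit in adjoining paragraphs of SAP 3.5 and conflict. Participants already in the pipeline enlarge the final sample whatever the conditional power was, including where the SAP's argument requires the sample to stay at 57.

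Overrun that does not depend on the interim result is harmless for a single-look test, but not for a fixed pair of levels. The pair 0.00998 and 0.02194 uses up 0.025 only at the information fraction for which it was solved. A larger final number lowers the correlation between the two looks, and the same two levels then spend more alpha. At stake is the stated one-sided 0.025, and so the defensibility of a final p-value just below 0.02194. Amendment 02 changed the alpha levels because simulations showed a Type I error above the nominal value, so the sponsor has already treated this kind of deviation as worth correcting.

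**Working it through.** **Inputs.** n1 = 43, n2 = 57, cap 77, zone limits 40% and 90%, z_alpha = 1.95996, z_beta = 1.28155 (SAP 3.5, Protocol 9.4); levels 0.00998 and 0.02194, i.e. c1 = 2.3271 and c2 = 2.0152. Overrun k, in completers above 57, is an assumption examined from 0 to 20.

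**1. The plan's own figures.** Classical two-look O'Brien-Fleming has c1 = C/√t and c2 = C, with correlation √t between looks. Solving for a total of 0.025 at t = 0.75 gives C = 2.0153 and levels 0.00998 and 0.02194, an exact match. At 43/57 = 0.754 the stated pair spends 0.02495.

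**2. The mechanism alone, no re-estimation.** Total alpha = 1 − P(Z1 < c1, Z2 < c2), correlation √(43/N). This gives 0.02495 at N = 57, 0.02511 at 58, 0.02567 at 62, 0.02624 at 67 and 0.02710 at 77.

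**3. Why the zone matters.** Given z1, the null probability of final rejection is 1 − Φ[(c2√N − z1√43)/√(N − 43)].
- z1 = 1 (unfavorable zone). N = 57: (15.214 − 6.557)/3.742 = 2.314, probability 0.0103. N = 67: (16.495 − 6.557)/4.899 = 2.029, probability 0.0213. It roughly doubles.
- z1 = 2 (promising zone). N = 57: (15.214 − 13.115)/3.742 = 0.561, probability 0.287. N = 67: (16.495 − 13.115)/4.899 = 0.690, probability 0.245. It falls.

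Increases in the promising zone are therefore conservative, and overrun in the unfavorable zone uses up that margin.

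**4. The full planned rule.** The conditional-power formula puts the promising zone at z1 from 1.593 to 2.254. Integrate the expression in step 3 over z1 < c1 and add 0.00998. Two choices are open:
- *Formula.* The printed re-estimation formulas differ: the denominator is √(n2 − n1) in Protocol 9.4 and √n2 − √n1 in SAP 3.5.
- *Overrun convention.* Either N is the larger of the target and 57 + k, or k is added to every target.

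| k | Protocol, larger-of | SAP, larger-of | Protocol, added | SAP, added |
|---|---|---|---|---|
| 0 | 0.02367 | 0.02330 | 0.02367 | 0.02330 |
| 5 | 0.02488 | 0.02455 | 0.02450 | 0.02420 |
| 6 | 0.02508 | 0.02477 | 0.02465 | 0.02436 |
| 8 | 0.02546 | 0.02518 | 0.02493 | 0.02466 |
| 10 | 0.02580 | 0.02556 | 0.02519 | 0.02494 |
| 20 | 0.02710 | 0.02710 | 0.02624 | 0.02606 |
| First k above 0.025 | 6 | 8 | 9 | 11 |

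Six million simulated trials using t-tests (Monte Carlo standard error 0.00006) run slightly higher and cross about one completer earlier: for example 0.02501 at k = 5 and 0.02518 at k = 6 in the first column.

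**5. What overrun is plausible.** The trigger is "An interim analysis will be performed after 43 participants (75%) have completed the study", and Protocol 4.4 defines completion as having "completed all periods of the study, including the last scheduled procedure shown in the SoA". That is Visit 8 on Day 56, although the endpoint is measured at Day 42. Assume a 4-week interim turnaround and the plan's 15% dropout. Completers from participants started by the decision are then about 43 + rate × (8 + 4) × 0.85. One start per week gives 53, two give 63 and three give 74. The 14 places between 43 and 57 are filled at 14/(12 × 0.85) = 1.4 starts per week.

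**The case against.** The strongest reply is that harmful overrun may never occur. The text treats overrun as a risk to mitigate, there are 14 places of headroom, and overrun after interim success is irrelevant because the primary endpoint is not tested again. Amendment 04 describes a high screen failure rate and a barrier to enrolment, which points to slow accrual; at one start per week the sample would not pass 57. The planned rule also starts below 0.025, so some overrun is absorbed. All of this stands, and it limits the size of the point. It does not supply the missing rule.

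A reader might infer three stronger claims that the documents do not support.
- *That the plan expects overrun past 57.* It allows for overrun but gives no accrual rate from which to predict it.
- *That one fixed number of overrun completers breaks the level.* The crossing runs from 6 to 11 under normal theory, because the two printed formulas differ and the overrun convention is not stated.
- *That fewer than 43 evaluable participants at the interim would also inflate the error.* Without re-estimation 40/57 gives 0.0256, but that is not the planned procedure. Under the zone rule with no overrun, the error is 0.0240 to 0.0244 at n1 = 40 and 0.0245 to 0.0249 at n1 = 38, all below 0.025. The SAP also defines n1 as the actual interim number.

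**Conclusion.** The point holds as a gap in the plan. The SAP's condition for Type I error control is not met once overrun takes completers past 57 outside the promising zone, and the Protocol's statement that no boundary correction is needed does not cover that case. All four readings exceed one-sided 0.025 within the range examined, reaching 0.0261 to 0.0271 at 20 above 57. At 10 above, the excess is at most 0.0008, and one reading is still under 0.025. These figures assume normal theory, n1 = 43 and overrun unrelated to the interim result. The size of any overrun is an assumption throughout. The change is worth making because it is cheap and easiest to defend if written before the interim.

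**What to change.** In SAP 3.5 and 5.4 and Protocol 9.1.1 and 9.4, keep 0.00998 at the interim. Add that, if completers exceed 57 because of overrun, the final critical value is recomputed from the actual n1 and the unadapted number (57 plus overrun) so that total one-sided alpha is 0.025. Qualify the Protocol's statement that no correction is needed.

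With n1 = 43 the final level becomes about 0.0212 at 62, 0.0205 at 67 and 0.0200 at 72. With the zone rule kept (Protocol formula, larger-of convention), total alpha is then 0.0243 at 5 above 57, 0.0246 at 10 and 0.0250 at 20, and no higher in the other readings. With t-tests instead of normal theory it can reach about 0.0251.

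The cost is wording and a slightly stricter final level. At a 3.5 mm Hg effect and SD 8.0, power goes from 95.0% to 94.8% at 10 above and from 96.8% to 96.5% at 20 above. A simpler alternative is to run the formal test on the target number only and report overrun participants as supportive, but that leaves data out of the formal test.

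State the overrun convention and reconcile the two printed re-estimation formulas. Optionally, trigger the interim at the 43rd valid EOT 24-hour recording. That matches the Completer Set and shortens the overrun window by about 2 weeks (Day 56 to Day 42).
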